Aim 1: Conduct a 2-arm pilot randomized clinical trial with patients referred for LCS who smoke (N = 80) to evaluate 7-day point prevalence abstinence rates and determine effect size estimates among participants who receive a standard intervention (single, brief counseling session at time of LCS) versus an enhanced medication and text messaging intervention (MTI; standard intervention + 8 weeks NRT + gain-framed messages with medication use reminders).

Hypothesis 1.1: Compared to the standard intervention, NRT and gain-framed text messaging will produce higher rates of smoking cessation at the end of Week 8.

Secondary Aim 2: To develop effect size estimates for rates of smoking cessation at the 3-month follow-up.

Hypothesis 2.1: Compared to the standard intervention, NRT and text messaging will produce higher rates of smoking cessation at the 3-month follow-up.

Exploratory Aim 3: To examine mediators and moderators of smoking cessation outcomes (i.e., nicotine dependence, medication adherence, positive lung finding from the scan [e.g., nodule is present]).

Hypothesis 3.1: Patients with greater nicotine dependence will have lower rates of cessation compared to those who have less nicotine dependence. Those who are more adherent with medication regimens in general (as assessed at baseline), as well as those who are adherent with the NRT regimen throughout the intervention, will have higher rates of cessation compared to those who are less adherent. Patients with a positive lung nodule finding after LDCT will be more likely to quit smoking than those who have a normal LDCT scan.

Exploratory Aim 4: To conduct exploratory analyses of cost-effectiveness of the intervention.

Hypothesis 4.1: I expect that the treatment intervention will be more cost-effective than standard counseling alone.

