A5. Mediators, Moderators, and Exploratory Analysis. This study will also evaluate important mediators and moderators of response to the intervention. Several message framing studies from both our group and others have found that nicotine dependence can moderate treatment efficacy.⁴²⁻⁴⁵ Thus, I will evaluate nicotine dependence as a moderator of treatment outcomes. Further, research has evaluated the effect of LCS findings (presence/absence of nodule) on smoking behavior,²⁶⁻²⁸ but no studies have evaluated how LCS findings moderate a smoking cessation intervention. Thus, I will carefully evaluate these factors and determine if LCS findings moderate outcomes. In addition, because consistent medication use may increase NRT efficacy,^{46,47} I will also evaluate medication adherence as a moderator and mediator of treatment outcomes. Finally, on an exploratory basis, I will evaluate the cost-effectiveness of the intervention compared to standard care.

B. Innovation:

1. This is the **first** study to test a gain-framed texting intervention in LCS. Although texting and gain-framed messaging have both been independently shown to be effective for smoking cessation, whether gain-framed text messages will improve quit rates for LCS patients is an empirical question. Delivery of gain-framed texts has the potential to enhance quit rates above those reported in prior studies because I plan to: 1) make the messages specific to a LCS population and 2) include reminders about medication use to increase the likelihood of medication adherence, and thus increase participant engagement with the intervention.
2. The model has the potential to be highly translatable to other LCS settings. I am proposing an easily translational behavioral (text messaging) and pharmacotherapy (NRT) intervention. A subsequent R01-funded full scale clinical trial could evaluate the intervention further for potential dissemination.
3. An assessment of mediators and moderators is also an innovative feature of this study as nicotine dependence, medication adherence, and lung screening findings are understudied in LCS patients.

C. Approach:

C1a. Preliminary Data on Gain-Framed Messaging

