Medication and Texting Intervention (MTI)	Standard counseling + 8 weeks of NRT + gain-framed text messages with medication reminders

smoker (defined as self-report any smoking in the past 7 days), 4) willing to be randomized, 5) English speaking; 6) access to device(s) that allows for text messaging and downloading apps; Exclusion: 1) unstable psychiatric/medical conditions such as suicidal ideation, acute psychosis, severe alcohol dependence, substance abuse, or dementia, 2) in the immediate (within 2 weeks) post myocardial infarction period, 3) serious arrhythmias, 4) unstable angina pectoris, 5) hemodynamically or electrically unstable, or 6) currently taking part in any other tobacco treatment program or using cessation medication (i.e., taking NRT or other cessation medications, enrolled in the Quitline, in another drug study). Exclusion criteria will be assessed through participant interview and/or medical record review.

Randomization. Given the goal of establishing an effect size, and the relatively small N in each group, we will use block randomization in an effort to ensure equal numbers in each treatment arm.⁵⁴ We considered using a stratified randomization procedure, but the aim of establishing effect sizes does not necessitate a randomization procedure that controls for covariates. If we observe imbalance on confounders by treatment group, we will adjust for these confounders in our analysis using regression modeling.

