If an eligible patient from MUSC Lancaster, MUSC Chester, MUSC Florence, or MUSC Columbia is interested in enrolling into the study, all study procedures will take place remotely. It is not feasible to perform study procedures in person due to the far distance from study staff, who are located at MUSC Charleston. Recruitment and all study procedures will follow the same procedures as described for MUSC Charleston sites, apart from using in-person methods. If the electronic medical record identified the patient as a smoker, or if the patient reports being a smoker at the time of their scan, the nurse practitioner will speak with the patient regarding the study and/or the patient will speak by phone with one of our study research assistants. The nurse practitioner will be given study flyers to hand out to eligible patients. Patients who express interest in the study will set up a virtual intake appointment with a research staff member. All participants recruited through these sites will complete the consent and baseline session using either 1) REDCap electronic consent (e-consent) combined with a phone discussion, 2) by mail combined with a phone discussion, or 3) a combination of these options.

All participants will have a smoking cessation counseling session with the lung screening nurse practitioner as part of standard clinical care. Of note, the treatment provided to study participants by the smoking cessation counselor in this study is a reimbursable service. This is important for 2 reasons: 1) NCI grant funds are not needed to support these high-cost services provided in this project, and 2) this increases the future translational possibilities of the intervention, as these methods will be sustainable at other cancer centers because insurance reimbursement will pay for these services. The counseling provided by the nurse practitioner will be based on practical counseling, which is a cognitive-behavioral, evidence-based, smoking cessation treatment modality.⁵⁵ The counseling session will last approximately 30 minutes, and all participants will be encouraged to set a quit date.

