NRT. In addition to the standard counseling described above, participants in the MTI arm will receive dual NRT (nicotine patch plus lozenge). An initial 2-week supply of 21 mg patches and 4 mg lozenges will be provided at the time of counseling or will be mailed to the participant within a week of randomization, and 3 additional 2-week supplies will be mailed out over the course of the subsequent 8 weeks. This mail-out model will allow us to assess participant use of the medications because participants will be contacted and asked how much NRT they used and if they would like to receive the next 2-week dose. Detailed information on each product, including instructions for use, will be provided in the take-home packet or emailed to the participant. We will inform patients about both single NRT use, as well as combined use, and participants will be given the opportunity to use the medications individually or together (participant choice, including none at all). Both patch and lozenge will be provided for four reasons. First, a number of studies demonstrate their efficacy when used singularly.⁵⁶ Second, they are both over the counter, increasing their utility within LCS settings where eligibility is minimal and instructions on use require nominal discussion. Third, whereas the patch provides a steady dose of nicotine throughout the day, the lozenge is used ad libitum and provides acute nicotine administration. These two mechanisms might appeal to smokers differently. Fourth, the majority of studies⁵⁷⁻⁶⁰ have shown that combined use of patch + lozenge is superior over placebo and single NRT products. Finally, the National Comprehensive Cancer Network Smoking Cessation Guidelines list combination NRT as first line pharmacotherapy. Those in the SC condition will receive standard counseling but no medications, and we will contact them every 2 weeks to inquire about use of any pharmacotherapies that they purchased on their own. At the time of patient contact regarding medications, research assistants will also assess point prevalence abstinence.

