See letter of support from consultant, [name], Director of the HCC Biostatistics Shared Resource. Sample size justification: Eighty participants (40 per group) will be enrolled. A sample size of 40 will allow us to establish estimates of abstinence with 95% confidence intervals (CI) for each arm, and to assess the precision in our estimates. The goal is to establish reasonably precise effect sizes to power a future study so we do not expect to achieve statistical significance in group comparisons. 95% CI and corresponding half widths for exemplar abstinence rates are provided in Table 2. With 40 patients per arm and an observed abstinence rate of 0.30, we can be 95% confident that the true abstinence rate is between 0.17 and 0.47 for that intervention.

Statistical Analysis: Aims 1 and 2 will be achieved by estimating abstinence rates with exact 95% CIs. Differences in rates and the 95% CIs for the differences will also be estimated. Baseline clinical and demographic variables will be assessed with summary statistics and reported by group, and compared to evaluate balance across groups. While the main aim of this pilot trial is to establish effect size estimates, we will also conduct a preliminary examination of between group differences in abstinence using logistic regression. With respect to exploratory analyses, logistic regression will also be implemented to evaluate effects of mediators and moderators of treatment on abstinence, and linear regression will be used to compare costs in the two arms. Given the pilot nature of this study, emphasis is on estimating effect sizes and variances and not statistical significance of associations. A sample size of 40 patients per group should provide sufficient preliminary data to guide me in my future research in this area.

Table 2. Example Effect Size Estimates

Observed Rate of Abstinence	95% CI	Half Width
0.50	(0.34,0.66)	0.16
0.30	(0.17,0.47)	0.15
0.10	(0.03,0.24)	0.10

C4. Recruitment, Feasibility, and Timeline

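### Exploratory Aim 4 is about cost-effectiveness, but its only stated analysis compares costs by arm, with no measure relating cost to abstinence and no definition of cost

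*Combined protocol and SAP*

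**What the plan says.** Exploratory Aim 4 in the Specific Aims is an analysis of cost-effectiveness, and Hypothesis 4.1 reads "I expect that the treatment intervention will be more cost-effective than standard counseling alone". Section A5 repeats the intention without a method: "on an exploratory basis, I will evaluate the cost-effectiveness of the intervention compared to standard care". The only analysis given for it is one clause in C3, Statistical Analysis: "linear regression will be used to compare costs in the two arms".

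Abstinence is analysed separately in C3, by rates with exact 95% intervals, rate differences with 95% intervals, and logistic regression.

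On what drives cost, Table 1 describes MTI as "Standard counseling + 8 weeks of NRT + gain-framed text messages with medication reminders". The counseling is common to both arms: "All participants will have a smoking cessation counseling session with the lung screening nurse practitioner as part of standard clinical care". After a first NRT supply, "3 additional 2-week supplies will be mailed out over the course of the subsequent 8 weeks", and these depend on the participant's wishes: "participants will be contacted and asked how much NRT they used and if they would like to receive the next 2-week dose". For the standard care (SC) arm, "we will contact them every 2 weeks to inquire about use of any pharmacotherapies that they purchased on their own". The Use of Pharmacotherapies assessment records amounts used and separates study-supplied from purchased products. No section gives a perspective, a list of cost components, unit costs or a time horizon for costs.

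**The concern.** Cost-effectiveness relates the extra cost of an intervention to its extra effect. A regression of cost on arm estimates only the first of these. Followed as written, Aim 4 would report a cost difference and nothing in it would bear on whether MTI is the better value, which is what Hypothesis 4.1 asserts.

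The outcome variable of the planned regression is also undefined. Whether it counts supplies sent or supplies used, staff time, counseling, or products that participants buy is left open. Those choices could be made after the data are seen, and they can change the answer considerably.

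**Working it through.** **The plan's own figures.** The documents state no cost or cost-effectiveness figure, so there is none to reproduce. The abstinence precision in Table 2 does reproduce: exact intervals for 20/40, 12/40 and 4/40 are (0.338, 0.662), (0.166, 0.465) and (0.028, 0.237), which match Table 2 after rounding.

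**Inputs from the documents.** 40 participants per arm (C3). Counseling in both arms, so it cancels from the difference. MTI adds 1 to 4 two-week NRT supplies and 3 × 7 × 8 = 168 texts per participant.

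**Assumptions.** Every dollar value, every abstinence count and the value λ placed on one additional abstainer.

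**1. The cost coefficient does not respond to the effect.** Net benefit = λ × (abstinence difference) − (cost difference). Take λ = $1,000, a cost difference of $100 and SC at 4/40.

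| MTI abstinent | Difference | Cost coefficient | Net benefit | Cost per extra abstainer |
|---|---|---|---|---|
| 4/40 | 0 | $100 | -$100 | undefined |
| 6/40 | 0.05 | $100 | -$50 | $2,000 |
| 10/40 | 0.15 | $100 | +$50 | $667 |
| 14/40 | 0.25 | $100 | +$150 | $400 |

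The stated analysis returns the same $100 in all four rows, while net benefit changes sign.

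**2. The definition of cost matters.** At 10/40 against 4/40, cost per extra abstainer = (mean supplies × price) / 0.15. One supply at $20 gives 20/0.15 = $133. Four at $60 give 240/0.15 = $1,600. That is a twelvefold range from two unfixed inputs.

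**3. How much a joint analysis adds to the uncertainty.** Take 10/40 against 4/40 and λ = $1,000. In MTI, let 10 participants each receive 1, 2, 3 and 4 supplies at $40 (mean $100, SD $45.3). Set text cost and SC incremental cost to zero.

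- Cost difference alone: 100 ± 1.96 × 45.3/√40 = $86 to $114.
- SE of the abstinence difference, using n − 1 variances: √(0.1875/39 + 0.09/39) = 0.0844, or $84.4 at λ = $1,000.
- Joint SE with abstainers spread evenly over supply groups (zero correlation): √(84.4² + (45.3/√40)²) = $84.7. The 95% interval for net benefit is 50 ± 1.96 × 84.7, or -$116 to $216.
- Joint SE at the extremes: $80.0 if all 10 abstainers took 4 supplies (correlation +0.77), and $89.1 if all took 1 (correlation -0.77).
- Abstinence interval alone (Newcombe, -0.019 to 0.314), scaled by $1,000 and reduced by $100: about -$119 to $214.

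The last interval nearly equals the joint one. At λ = $200 the picture differs: the SE is $16.9 from abstinence alone, against $13.5 to $22.1 jointly across the same two extremes.

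**4. Why the ratio should be a point estimate only.** In bootstrap resamples of this example, just under 5% had no abstinence gain. The ratio is undefined or negative there, so a ratio interval would be hard to interpret. Net benefit avoids this.

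**The case against.** The strongest reply is that this is an unstated last step, not a wrong analysis. C3 plans the cost comparison and the abstinence difference with its interval, A5 says the two are to be considered together as cost-effectiveness, and one division gives a cost per additional abstainer. This largely stands, and it is why the point is minor. It does not remove the gap: no section commits to the step, and the quantity to be divided is not defined.

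A reader might infer that, without a joint analysis, the plan would seriously misstate uncertainty. The documents do not support that. In the illustration the interval already planned for abstinence, put into dollars, gives almost the joint result (SE $84.4 against $84.7). Correlation between refills and quitting is plausible because refills are on request, but it moves the SE only to $80.0 or $89.1. It matters clearly only when λ is low relative to cost.

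A reader might also infer that the sign of the cost difference is fixed in advance. That is expected from a programme perspective, because MTI adds components to what SC receives. The documents name no perspective, and they ask both arms about products bought privately. If those purchases counted, the sign would not be settled beforehand.

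Finally, Aim 4 is exploratory in a pilot that stresses estimation over significance, and no section says that a later trial will plan an economic analysis. That limits the consequence.

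**Conclusion.** The point holds as a minor gap in specification. The one analysis stated for Aim 4 cannot address Hypothesis 4.1, because it takes no account of abstinence, and cost is undefined. In the illustration the same $100 coefficient accompanies net benefit anywhere from -$100 to +$150. Those figures rest wholly on assumed costs, abstinence counts and λ; the documents supply only the 40 per arm, the 1 to 4 supplies and the 168 texts.

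The gain from a change is mainly an analysis that answers the stated hypothesis, not a large change in uncertainty. Aims 1 and 2 are unaffected, and nothing here should be read as a criticism of how they are analysed.

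**What to change.** Replace the cost clause in C3, Statistical Analysis, with:

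> Aim 4 (exploratory): incremental cost, the difference in 7-day point prevalence abstinence at Week 8, and incremental cost per additional abstinent participant (point estimate) will be reported. Uncertainty will be given by regressing net benefit (λ × abstinent, minus cost) on arm over a range of λ fixed before analysis, with a participant-level bootstrap within arm. Cost: programme perspective over 8 weeks, applying listed unit costs to NRT supplies sent with postage, text messaging, counseling, and staff time for the refill contacts that are part of delivering MTI. Participant-purchased products will be added in a sensitivity analysis.

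The bootstrap should resample each participant's cost and abstinence together.

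This costs one paragraph and a unit-cost table. The study mails the refills itself, so it knows how many supplies were sent; abstinence and private purchases are already collected. No new visit or participant question is needed. The downsides are that unit costs, including a staff time per refill contact, must be assigned, and that intervals will be wide at 40 per arm. The results should therefore stay labelled exploratory.

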These two week check-ins will occur either by phone or through MUSC REDCap's automated survey feature. Surveys can be automatically sent to patients for each two-week follow-up and patients can fill out the questions to indicate whether they would like more medications to be mailed to them. After the completion of the two-week check-ins, patients will be sent an Amazon gift code as a form of compensation. The payment will be as follows: \$10 for each completed two-week check-in and \$25 at the completion of the 3-month visit. If a participant completes at least 3 of the 4 check-ins, a \$30 bonus amazon gift code will be provided.

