
Follow-up: Participants will complete either online or paper assessments (no return clinic visit) at the end of treatment and 3 month follow-up session. Point prevalence abstinence will be established. At the 3-month follow-up all of the participants will also complete a biochemical verification of abstinence (see Outcome Definition below). Participants will be paid \$25 in the form of Amazon gift card codes for completion of the 3 month follow-up interview.

Assessments (Items with an asterisk will be tested as a mediator or moderator):

Demographic, Smoking History, and Current Medications Questionnaire: This questionnaire will obtain: 1) basic demographic information and 2) basic smoking status and history.^{12,15,62}

Tobacco Use Calendar (Timeline Followback): This standardized, validated, and reliable experimenter-administered rating scale⁶³⁻⁶⁵ will be used to obtain quantity and frequency estimates of cigarette consumption for a 30-day period prior to treatment and to retrospectively record daily use at each participant contact point.

***Fagerström Test for Nicotine Dependence (FTND) and Heaviness of Smoking Index (HSI):** The FTND is a commonly used scale for the measurement of severity of dependence on nicotine.⁴⁸ The HSI assesses 2 items from the FTND regarding amount smoked and time-to-first-cigarette.⁴⁹ The HSI has been shown to predict both behavioral and biochemical indices of smoking.⁴⁸⁻⁵⁰ In line with findings from our previous research^{42,43} and from other groups,^{66,67} we plan to test both the FTND and HSI as moderators of treatment.

***Medication Adherence Questionnaire (MAQ):** The MAQ is a self-report instrument composed of four items that assess participants’ history of medication adherence,^{68,69} which may moderate treatment outcomes.⁷⁰ Using the MAQ score, medication adherence will be assessed as a baseline moderator of treatment outcome.

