***Use of Pharmacotherapies:** We will determine the amount and frequency of NRT used (per product), and will also determine use of products we provide vs. purchase of additional products. For all participants, at each refill or contact point during the 8-week time frame, we will ask how many total patches and lozenges were used since the last contact, and how many were used each day. I will also incorporate a text-message based medication use assessment, as previously described. This novel approach will allow us to collect a daily medication diary from each participant, instead of relying on retrospective report. After calculating a percentage of medications taken, medication adherence will be assessed as a mediator of treatment outcomes.^{70,71}

Attitudes Towards NRT: Attitudes towards NRT may differ depending on the amount of NRT they elect to receive, the types of NRT selected, and the patient experience with the medication. We will assess 1) positive, and 2) negative attitudes towards NRT, as well as 3) general knowledge of NRT.^{32,72-76}

Motivation and Confidence to Quit: We will assess motivation and confidence to quit smoking using our modification of the Contemplation Ladder^{77,78} which assesses readiness to quit in the next month.

*Findings from screening: Lung screening findings will be defined as pulmonary findings (nodule, cancer, emphysema, enlarged lymph nodes) and coronary findings (calcification).

Adverse Events: We will assess adverse events at each NRT refill time point for the MTI group. For the SC group, we will ask about adverse events at each contact point after LCS. We will grade and report the severity of adverse events as described in Protection of Human Subjects. Participants who have significant side effects from NRT use will be encouraged to discontinue NRT use immediately.

Texting Satisfaction Survey: We will assess participant satisfaction with the texting intervention, including frequency, timing, and content of the text messages.

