Safety Monitoring. This protocol presents minimal risks to participants. The study involves receiving gain-framed text messages and NRT, and to complete follow-up interviews. The only risks that can be anticipated from this study is loss of confidentiality, and this will be protected using the procedures described in the "Sources of Materials" section above. In addition, participants may experience side effects from NRT (as previously described). Nonetheless, because we anticipate that behavior change (which will pose minimal risk to participants) will be a product of participating, we have developed a safety monitoring plan to report adverse events resulting from behavioral changes.

Monitoring to identify adverse events. Prior to implementing the randomized study, research staff will be trained to identify adverse events. Research staff will be instructed to provide [name] with a detailed description of the event. [name] will grade the event in conjunction with [name] within 24 hours. The following additional individuals will be informed immediately of serious adverse events: (a) the mentoring committee; (b) the National Cancer Institute (NCI); and (c) the MUSC IRB. All of these individuals and committees will receive a copy of a SAE Form within 48 hours, at which point a decision will be made whether to convene a meeting.

Plan for grading adverse events. Serious Adverse Events (SAE). The FDA's definition of serious adverse events (21 CFR 312) will be used. Serious Adverse Events include any untoward medical occurrence that at any dose results in death or the immediate risk of death, hospitalization or the prolonging of an existing hospitalization, persistent or significant disability/incapacity or a congenital anomaly/birth defect, new cancer, or medication overdose. Adverse events will be defined and graded for risk as follows:

Coding of Severity:

0 = No adverse event or within normal limits

1 = Mild adverse event

2 = Moderate adverse event

3 = Severe, resulting in psychiatric or medical hospitalization

4 = Life-threatening adverse event

5 = Fatal adverse event

Coding of Attribution will be made for adverse events grade 3 and above (ie, serious adverse events):

1 = Unrelated to study interventions

2 = Unlikely relationship to study interventions

3 = Possible relationship to study interventions

4 = Probable relationship to study interventions

5 = Definite relationship to study interventions

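### Every stated way of finding adverse events relies on the participant's own report, so a death or lasting incapacity has no planned route into serious adverse event reporting, and enquiry differs by arm

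*Combined protocol and SAP*

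**What the plan says.** The procedure for finding adverse events is in section C2, Assessments, under Adverse Events. For the intervention arm: "We will assess adverse events at each NRT refill time point for the MTI group". For standard care: "For the SC group, we will ask about adverse events at each contact point after LCS".

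The contacts are described under Intervention Procedures. "These two week check-ins will occur either by phone", or through an automated REDCap survey. There are four of them ("If a participant completes at least 3 of the 4 check-ins", a bonus is paid). A refill depends on a reply: "participants will be contacted and asked how much NRT they used and if they would like to receive the next 2-week dose". Under Follow-up, "Participants will complete either online or paper assessments (no return clinic visit) at the end of treatment and 3 month follow-up session". At the Lancaster, Chester, Florence and Columbia sites everything is remote.

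Protection Against Risk, item (c), also foresees a participant reporting an adverse effect of NRT.

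The Data and Safety Monitoring Plan has a paragraph on identifying adverse events, which begins "Prior to implementing the randomized study, research staff will be trained to identify adverse events" and goes straight on to grading and notification. Its SAE definition includes death, hospitalization and persistent or significant incapacity. SAEs are to be reported within 24 hours, with a written report within 48 hours.

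The medical record is already used for another purpose: "Exclusion criteria will be assessed through participant interview and/or medical record review". Study staff have access to protected health information.

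**The concern.** The reporting deadlines can start only once staff learn of an event. Every described route to that knowledge is the participant answering a contact or volunteering a report. For a death, the event itself closes the route. For lasting incapacity it probably does. The missing safety data then depend on the safety outcome, and the SAE count is biased low.

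The semiannual report to the mentoring committee lists retention and adverse events, and the committee uses it to recommend whether the protocol continues. The plan has no step for finding out why someone stopped replying. From that report the committee could not tell a death from ordinary drop-out.

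There is also an asymmetry between arms. SC is asked at every contact. MTI, read literally, is asked only at refills, and NRT use is optional. On that reading an MTI participant who stops NRT, possibly because of side effects, has no further refill point at which to be asked.

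**Working it through.** **Figures in the plan.** None on this point. Section C3 sizes the study for abstinence only, and no SAE or non-response rate is stated. The rates below are assumptions shown over a range.

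**Inputs from the documents.** 80 participants, 40 per arm. Four check-ins in 8 weeks and a 3-month follow-up. One initial 2-week NRT supply and three mailed supplies.

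**Assumptions.** SC contacts at weeks 2, 4, 6, 8 and 13, counting the 3-month follow-up as a contact at which events are asked about. Events uniform over 13 weeks. Probability *s* of no reply at each contact, independent between contacts. An event is lost only if every later contact fails.

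**Share of SAEs never reported, SC schedule.** Events in weeks 0-2 have five later contacts, weeks 2-4 four, weeks 4-6 three, weeks 6-8 two, and weeks 8-13 one:

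share = [2(s⁵ + s⁴ + s³ + s²) + 5s] / 13

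- s = 0.2: (0.100 + 1.0)/13 = 0.085
- s = 0.3: (0.255 + 1.5)/13 = 0.135
- s = 0.4 (0.2 doubled): (0.520 + 2.0)/13 = 0.194
- s = 0.6 (0.3 doubled): (1.567 + 3.0)/13 = 0.351

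This gives about 8%-14%, or 19%-35% if affected participants are twice as likely to be silent. Most of the loss comes from weeks 8-13, which have a single contact.

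**Deaths.** Here s is 1 at every later contact, so the share is [2(4) + 5]/13 = 1. It falls below 100% only if someone else tells the study.

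**Scale in participants.** If the 3-month SAE risk is 2%-6% (assumed), 80 × 0.02 = 1.6 to 80 × 0.06 = 4.8 SAEs are expected. Applying the shares above to all 80, the expected number missed runs from 1.6 × 0.085 = 0.1 to 4.8 × 0.351 = 1.7.

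**Could a death occur?** Section C1b cites cumulative mortality of 5.9% (very low dependence) to 11.0% (very high dependence) in a screening cohort, without the follow-up time. Take 3 to 7 years as an assumption, with hazard h = -ln(1 - c)/T and 3-month risk p = 1 - exp(-0.25h):

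- c = 0.059, T = 7: p = 0.0022, expected deaths in 80 = 0.17, chance of at least one = 16%
- c = 0.110, T = 3: p = 0.0097, expected deaths in 80 = 0.77, chance of at least one = 54%

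**Enquiry by arm.** Three mailed supplies after the first place the refill points at about weeks 2, 4 and 6. On the literal reading, MTI is last asked at week 6, so 7 of 13 weeks (54%) fall after the last enquiry. On the SC schedule assumed above, none do.

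**The case against.** The gap is inferred from silence. The safety plan does not exclude record review, volunteered reports are foreseen, and scan findings, including cancer, are collected, so a new cancer (a listed SAE) may have another route. Consent pages are not in the public copy and might cover an alternate contact or record follow-up. This stands: the point can be made only about the *stated* sources.

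A reader might go further in four ways that the documents do not support.

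- That all of grades 3 to 5 are the events most likely to be missed. This is sound for deaths. For a hospital stay it is not shown, because a discharged participant can report at a later contact. Incapacity belongs to the SAE definition and is not one of the grades.
- That such events would be recorded as loss to follow-up. No section says how non-responders are classified, and retention and adverse events are separate items in the semiannual report.
- That MTI, with its texts and refills, would detect more. SC is also contacted every 2 weeks and is asked about adverse events each time. The texts are described as covering craving, medication use and smoking, not adverse events.
- That 20%-30% silence at one contact means 20%-30% of SAEs lost, or 40%-60% if doubled. This treats one missed contact as permanent and ignores the later ones.

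It is also fair to say that this is a small pilot of over-the-counter NRT and texting, described as minimal risk. It has paid check-ins and no planned safety comparison, so no planned estimate is biased. But the plan commits to reporting every SAE within set times, and low risk does not supply a way of detecting one.

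**Conclusion.** The point holds for the stated procedure. Followed as written, a death or lasting incapacity has no participant-independent route into SAE reporting, and the semiannual report has no means of separating such events from non-response. This conclusion needs no assumed rate.

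The size cannot be fixed from the documents. The 8%-14% and 19%-35% figures rest on assumed silence rates, contact weeks and independent non-response. Persistent drop-out would raise them, as would refill-only enquiry in MTI. If SC participants are not asked about events at 3 months, the SC figures rise too. For deaths the share is close to 100%.

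The difference in enquiry between arms follows from the text read literally. Adverse event counts would then not be comparable between arms, even among people who reply.

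**What to change.** Add to the paragraph on identifying adverse events: *At the 3-month point, staff will review the MUSC medical record and vital status of every participant in both arms for death, hospitalization and any other SAE criterion since randomization. The reporting clock for an event found this way starts at the review.*

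An earlier look-up after a missed check-in may be added so that events are found sooner. SAE counts should still rest on the uniform 3-month review, because a search triggered by non-response could differ in intensity between arms.

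Ask about adverse events at the same contact points in both arms, whether or not an MTI participant requests a refill. In the semiannual report, show deaths and hospital stays separately from loss to follow-up, by arm.

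Cost: 80 record reviews of a few minutes each by staff who already have access, plus any look-ups after missed check-ins. Confirm that the consent and HIPAA authorization cover this use. No endpoint, sample size or treatment changes. Events outside the MUSC record may still be missed, and nothing in the documents shows that this would be equal between arms. A consented alternate contact would narrow that gap.
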